## **5.7 Adherence/Compliance**

5.7.1 Participants will be considered compliant if they have taken 80% of the prescribed doses and have missed no more than 3 doses in the final 14 days prior to surgery.

5.7.2 The participants will be asked at registration if they would like to utilize a phone application in place of paper forms. According to subject preference, participants will either utilize phone application or fill out paper forms daily to monitor compliance. For participants utilizing the phone application, the study coordinator will be notified after 2 days of missed entries. For individuals using paper forms, email messages will be sent daily for the first week; in following weeks, messaging will be targeted to women having difficulty remembering their dose.

5.7.3 Capsule counts and weighing of gel dispensers will be performed at the conclusion of therapy. Drug and metabolite levels will be measured in blood and tissue on the last day of administration. Prescribed doses include one capsule per day, or one pump of the gel on each breast per day. If the capsule count consumed by the subject is lower than  $D*80\%$ , or the amount of gel consumed is less than  $2D*80\%*[m - sd(m)]$ , where D is the number of days between visits, m and  $sd(m)$  are the mean and standard deviation of the weight of one pump of the gel provided by the manufacturer, or if more than three doses of therapy are missed during the final 14 days, the subject will be considered non-compliant. For subjects with only one breast, the lower limit of the amount of gel consumed for compliance is  $D*80\%*[m - sd(m)]$ . All participants who receive a study agent for any period of time will be evaluable for toxicity. Treatment compliance assessment will be based on the active ingredient component of the treatment regimen, i.e. the pill count for the Oral Tamoxifen group and gel dispenser weight for the 4-OHT gel group.

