
**Adverse Events.** AEs will be assessed using CTCAE. Worst grade toxicity for each AE type will be summarized by arm using descriptive statistics. For each AE type, proportions of patients experiencing toxicity of any grade will be compared between arms using Fisher's exact test.

**Treatment Compliance.** Compliance will be defined as described in Section 5.7. Each patient will be determined as compliant or non-compliant for each treatment component (capsules compliance and gel compliance). Treatment compliance rates based on active ingredient component will be summarized using proportions, and compliance rates will be compared between arms using Fisher's exact test. In addition, in order to determine whether compliance is different for capsule vs. gel administration, within-subject differences in treatment component compliance will be analyzed using the McNemar test among all patients, regardless of treatment arm.

**Subgroup analysis.** Exploratory analyses will be conducted by menopausal status (pre or peri-menopausal vs. post-menopausal). Descriptive statistics will be used to summarize study endpoints by group. In addition, linear regression models as described above will be used with the addition of menopausal status and possibly its interaction with treatment as predictors. Model-based linear contrasts will be constructed to test relevant treatment noninferiority or superiority hypotheses within subgroups. Similar analyses will be conducted in the subgroup of women with invasion in the post-treatment surgical sample.

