**Study Diary Part II**

Protocol Number  
Subject ID  
Site

Name  
Start date

End Date

Day	Monday	Tuesday	Wednesday	Thursday	Friday	Saturday	Sunday
Date							
Time							
How many hot flashes in the past 24 hours above your normal experience?	0 1-5 6-10 11-15						
Night sweats in the past 24 hours above your normal experience?	Yes No						
Did you apply your gel to both breasts, a total of 2 complete pumps (1 complete pump per breast?)	Yes No						
Did you discard any pumped doses of gel?	Yes No						
If yes, how many pumped doses did you discard?							
Did you take your capsule?	Yes No						
Are you having a period?	Yes No						

Study Coordinator's Signature/Date

To be repeated, for each week, until end of intervention

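### The gel-versus-capsule compliance comparison reduces daily records to compliant/non-compliant before a McNemar test, which can cost a large share of its power; a paired analysis of days taken should lead

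*Combined protocol and SAP*

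**What the plan says.** Section 13.5.4 (Treatment Compliance) sets the aim of finding out whether compliance differs between capsule and gel administration. The outcome is binary: "Each patient will be determined as compliant or non-compliant for each treatment component (capsules compliance and gel compliance"). The test is McNemar's: "within-subject differences in treatment component compliance will be analyzed using the McNemar test among all patients, regardless of treatment arm". The variant (asymptotic, mid-p or exact), the alpha level and the sidedness are not stated for this test.

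Section 5.7.1 defines compliance by two conditions that must both hold. A participant must "have taken 80% of the prescribed doses and have missed no more than 3 doses in the final 14 days prior to surgery".

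Finer data are collected. Under Section 5.7.2, "participants will either utilize phone application or fill out paper forms daily to monitor compliance". Study Diary Part II (Appendix B) asks each day "Did you apply your gel to both breasts, a total of 2 complete pumps" and "Did you take your capsule". Section 5.7.3 adds two quantitative measures: "Capsule counts and weighing of gel dispensers will be performed at the conclusion of therapy".

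Compliance is not among the objectives in Section 1, and the plan gives no power, expected rate or effect size for this comparison.

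**The concern.** McNemar's test uses only women who are compliant on one product and non-compliant on the other. A woman on treatment for 49 days may miss up to 0.20 × 49 = 9.8 days of a product before failing the 80% condition. If she misses 8 gel days and 1 capsule day, with no more than 3 gel misses in the last 14 days, she is compliant on both and adds nothing to the test, although her record plainly favours the capsule.

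The 80% rule is needed to define the per-protocol set. Nothing in the plan requires it for the question of which product is taken more reliably. Section 2.3.1 says that trials must show transdermal delivery to be acceptable to women, so this comparison has some bearing on the case for the gel. A non-significant result from a weak test, with no estimate of the difference beside it, would tell the reader little.

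**Working it through.** **No plan figure exists for this comparison.** The plan's only power figure, 80.5% for the Ki-67 endpoint, reproduces (n = 40 per arm, margin 2.6, SD 5.4, one-sided alpha 0.10, noncentral t with 78 df), but it says nothing about compliance.

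**Inputs from the documents.** 90 women evaluated for study endpoints (Section 3.2), with up to 100 starting; 28 to 70 days on treatment (Section 3.4); both conditions of the Section 5.7.1 rule.

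**Assumed, because the documents are silent.** Two-sided alpha 0.05; treatment length uniform over 28 to 70 days; mean capsule miss rate 2% to 15%; beta-distributed miss rates between women with intraclass correlation (ICC) 0.05 to 0.30; gel–capsule correlation 0.3 to 0.9. The 10% attrition in Section 3.2 covers non-compliance together with logistical losses and is not specific to capsules, so it is only a loose guide.

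**Tests.** Let b be the number of women failing gel only and c the number failing capsule only.
- Asymptotic McNemar: (b − c)²/(b + c) compared with 3.84.
- Exact McNemar: binomial(b + c, ½). Five discordant women all in one direction give 2 × 0.5⁵ = 0.0625; six give 2 × 0.5⁶ = 0.031. Fewer than six can never reach 0.05.
- Paired t: d = gel days missed/D − capsule days missed/D for each woman, with D her days on treatment; t = mean(d)/(SD(d)/√n).

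**Fixed differences, lapses spread over women, n = 90:**

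| Days missed, capsule vs gel | ICC, correlation | Paired t | McNemar asymptotic | McNemar exact |
|---|---|---|---|---|
| 3% vs 5% | 0.05, 0.3 | 81% | 16% | 4% |
| 5% vs 8% | 0.15, 0.7 | 84% | 35% | 27% |
| 10% vs 15% | 0.15, 0.3 | 80% | 56% | 48% |
| 10% vs 20% | 0.15, 0.3 | 100% | 98% | 97% |

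The second row can be checked by hand. About 8.1% of women fail the capsule rule and 14.3% the gel rule, so b − c is expected to be 90 × (0.143 − 0.081) = 5.6. The asymptotic test then needs b + c below (5.6/1.96)² = 8.2, so c must be below (8.2 − 5.6)/2 = 1.3. Nearly every woman who fails the capsule rule would also have to fail the gel rule. Power below 50% is what one would expect.

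The first three rows change little with the sample size. At n = 100 they give 85%, 88% and 84% for the t-test against 15%, 39% and 59% for asymptotic McNemar.

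**Differences set so that the paired t-test has 80% power, 72 scenarios.** Median McNemar power is 44% asymptotic (range 3–66%), 42% mid-p (1–65%) and 34% exact (0–59%). The medians keep 44/80 = 55%, 42/80 = 53% and 34/80 = 43% of the t-test's power. A loss of more than half occurs in this many scenarios:

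| Capsule miss rate | Asymptotic | Mid-p | Exact |
|---|---|---|---|
| All scenarios | 30/72 | 33/72 | 47/72 |
| 5% or less | 22/36 | 23/36 | 30/36 |
| 10–15% | 2/24 | 4/24 | 10/24 |

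**A second model.** This takes 49 days, logit-normal miss probabilities (SD 1.0, correlation 0.5), a capsule mean set so that 10% of women miss more than 20% of days, and the full Section 5.7.1 rule. With a gel shift of 0.35 on the logit scale, McNemar has 26% (exact) or 34% (asymptotic) power against 67–69% for a paired analysis of missed days. With a shift of 0.5 it is 66% (asymptotic) against 93%. Type I error of the paired analysis is near 5%.

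**If the difference comes from women stopping the gel outright** (5–10% of women, 16 scenarios), asymptotic McNemar keeps 58–105% of the paired t-test's power. The loss exceeds half in 0/16 scenarios (exact: 7/16). Asymptotic McNemar beats the Wilcoxon signed-rank test in all 16. In one run of this kind, power was 47% for the paired t-test, 28% for asymptotic McNemar and 21% for Wilcoxon.

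**The case against.** McNemar's test is a valid test of the plan's own definition of compliance. The comparison is neither an objective nor a powered endpoint, and nothing in the plan says that a non-significant result will be read as equal adherence. All of that stands, and it limits how much the point matters.

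A reader might infer that the plan throws away more than half its power in most situations. The documents do not support this. They give no miss rates, spread, correlation or expected difference, and they do not name the McNemar variant. Over the full 72-scenario grid a loss of that size is a majority result only for the exact test (47/72), and with fixed differences it is a minority result for both variants run (9/36 asymptotic, 12/36 exact).

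The alternative is not uniformly better either. A rank test would do worse than asymptotic McNemar if some women simply stop the gel. This stands, and it is why the mean paired difference should lead, with the rank test as a sensitivity analysis.

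The 8-in-49 example depends on the second condition of the rule. If the eight misses fall at random, about 15% of such women have four or more in the last 14 days (hypergeometric) and are non-compliant on gel after all. Most are still classed compliant on both products, and applying the full rule changes the power figures little.

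Finally, the diary is self-report and may have gaps, whereas Section 5.7.3 relies on counts and weights. This stands as a limitation. The gel weight has its own bias: Appendix B has women prime each new canister and discard mis-pumped doses, and by weight that gel counts as used. The weight cut-off is also lowered by one SD per pump, with no matching allowance for capsules.

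**Conclusion.** The point holds. Section 13.5.4 asks whether gel and capsule are taken equally well, then discards most of the daily information that would answer it. The loss of power is around half or more when adherence is high and lapses are spread over many women. It is smaller when the difference is large, when miss rates are higher, or when the difference comes from women stopping the gel. These sizes rest on assumed miss rates, spread and correlation, a two-sided alpha of 0.05, and diary entries that reflect true use; the documents fix none of these.

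It would go too far to read this as a flaw in the efficacy analysis or in the per-protocol definition. The comparison is a supporting one, the Section 5.7 classification serves its purpose for the per-protocol set, and the primary Ki-67 endpoint is untouched. This is a worthwhile, low-cost improvement.

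**What to change.** In Section 13.5.4:

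- Make the main capsule-versus-gel comparison the within-woman difference in the proportion of prescribed days taken, from the diary or app, among all women who started treatment. Report the mean paired difference with a 95% CI and a two-sided paired t-test, with the Wilcoxon signed-rank test as a sensitivity analysis.
- Keep McNemar on the Section 5.7 classification as a supportive analysis, and name the variant and alpha. Keep that classification for the per-protocol set.
- State beforehand how blank diary days are counted, and how the both-breasts diary item is scored for women with one breast, whom Section 5.7.3 anticipates.
- Show capsule-count and gel-weight percentages beside the diary result, with a note that primed and discarded pumps count as gel used by weight.

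The cost is SAP wording and one further analysis of data already collected. The downside is that the main comparison then rests on self-report, which the counts and weights can only partly check.

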### 13.6 Reporting and Exclusions

**Reporting and Exclusions:** We expect that 80 subjects will have complete data on the primary endpoint, while about 28 subjects out of 108 (roughly 25%) will be excluded because of not starting study medication, study drop-out, or insufficient DCIS in the surgical specimen. Main analysis will be based on the complete data. Additional descriptive analysis may be performed to see if drop-outs show a systematic property. Thus, we expect the 20% of data missing values will be studied to determine possible patterns and dependence with other relevant variables.

### 13.7 Evaluation of Toxicity

All participants will be evaluable for toxicity from the time of their first dose.

### 13.8 Evaluation of Response

13.8.1 *Intent to treat analysis* All samples from all subjects who receive drug will be evaluated and included in the primary analysis, which will be based on intent to treat principle. Per protocol analyses will then be performed as described in Section 8.4.2.

13.8.2 *Missing data* The general approach will be to perform a complete case analysis when the missingness rate is low, and when a missing completely at random (MCAR) or missing at random (MAR) assumption can be reasonably made. To determine whether such assumptions are reasonable, reasons for data missingness will be documented, and clinical and demographic characteristics will be compared between patients with and without missing data for each particular endpoint. If the missing data rate is relatively high but the MAR assumption is reasonable, complete case analyses will be done and carefully interpreted given high missing data rates. To assess the robustness of findings, sensitivity analyses will be performed, including covariate-adjusted regression models, and “best-worst” analyses where all missing values are replaced by either best or worst values for categorical outcomes, and by highest or lowest observed values for continuous outcomes. Multiple Imputation. If data is missing for > 10% of the entries, multiple imputation may be performed via a semiparametric approach based on association between continuous biomarker variables, between binary variables, and between continuous with binary and categorical data [see refs 52-55]. In these approaches, missing data are filled in by plausible values obtained from joint modeling. Observed data are first transformed to normally distributed values so as to satisfy the normality assumptions of the joint modeling approach. Imputed data are then transformed back onto the original scale of the observed data. Imputations are run until convergence criteria are met depending on pairwise correlations between the variables imputed. Performance of the multiple imputation will be assessed via standardized biases (< 50% being acceptable), coverage rates (> 90% being acceptable), small root mean square errors, and average widths of 95% confidence intervals for the estimates from imputed data being comparable to the widths of 95% confidence intervals for the original data pertaining to the pairwise correlations. The goal for the imputed data is to satisfy the assumptions from our power analysis and ensure the convergence of parameter estimation.

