### 13.4.2 Proposed Sample Size:

A total of up to 108 women will be accrued and randomized over an 18 month period (1:1 oral:gel), with no more than 100 women to start intervention. Assuming a 20% rate of nonevaluable samples due to insufficient residual DCIS, we expect a total of 80 subjects evaluable for the primary endpoint of Ki67, comparing pre to post-therapy samples. Primary analysis will be conducted in all randomized evaluable patients per intent-to-treat. Additional analyses will be conducted in the per-protocol population of patients who were treatment-compliant as defined in Section 5.7. Adverse events will be evaluated in all patients who received at least one treatment dose.

Sample size calculations: From previous publication (Table 2, Lee et al.) we have an average percent staining for Ki67 at baseline of 7.5% with  $SD=5.4\%$ . Assuming within-subject correlation between pre- and post-treatment values is  $\rho=0.5$ , the pooled  $SD$  of the changes will be  $SD_p=5.4\%$ . A 50% drop (from 7.5%) gives 3.75% while a 35% drop (from 7.5%) gives 4.9% in Ki67 staining. If the drop in the 4-OHT group is non-inferior to the standard of care, we would see it. We use compatible  $SD$  from Table 2 in Lee et al, obtaining for the 4-OHT group adequate power to detect a non-inferiority of 35% or bigger drop with a small type 1 error of 10%. Now 2.6% staining. Thus, with a non-inferiority margin  $M=2.6\%$ , sample size of  $n=40$  evaluable patients per arm will provide 80.5% power with one-sided  $\alpha = 0.10$  significance level to detect non-inferiority based on a two-sample equal variance t-test comparing changes in Ki67% staining. Calculations were done using PASS 11.

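### Section 13.8.2 aims imputed data at the power-analysis assumptions and sets bias and coverage limits that cannot be checked on the trial's own missing values; a fixed imputation model should replace both

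*Combined protocol and SAP*

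**What the plan says.** Section 13.8.2 (Missing data) makes complete-case analysis the general approach. It keeps that approach when missingness is relatively high, provided missing at random is reasonable, and adds covariate-adjusted and best-worst sensitivity analyses. Imputation is then permitted: "If data is missing for > 10% of the entries, multiple imputation may be performed". The method is described as a semiparametric joint model of associations among continuous, binary and categorical variables. The text does not list the variables in the model, the number of imputations, the pooling rule or the analysis to be run on the imputed data.

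Four performance checks follow. Two have numerical limits: "Performance of the multiple imputation will be assessed via standardized biases (< 50% being acceptable), coverage rates (> 90% being acceptable". The others are small root mean square error and interval widths comparable with those from the original data. Only the width check has a stated target, the pairwise correlations. The paragraph then says: "The goal for the imputed data is to satisfy the assumptions from our power analysis", and joins to this the aim of convergence.

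Section 13.6 bases the main analysis on complete data. It expects 28 of 108 randomised women to be excluded and adds: "Thus, we expect the 20% of data missing values will be studied".

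**The concern.** An imputation is valid if it gives sound inference under a stated assumption about why data are missing. It need not resemble the planning values. If the goal means matching the assumed mean, SD or correlation, it is circular, because the observed data may properly differ from the design. If it means reaching the planned N, imputation creates no new information. Neither reading makes it a proper target.

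The bias and coverage limits have a different fault. Both compare an estimate with the truth, and the truth is unknown for the trial's own missing values. They could be computed in a simulation, but the plan describes none and does not name the treatment effect (gamma in section 13.4.3) as the parameter to be checked.

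The choice to impute and the imputation model are therefore left open until the data are in hand. In a non-inferiority trial, a model that blurs the arms favours the claim under test. At stake is the credibility of any imputed result offered to support the complete-case finding.

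**Working it through.** **Inputs.** From section 13.4.2: margin M = 2.6 points, SD of change 5.4, 40 evaluable per arm, one-sided alpha 0.10. From sections 13.2 and 13.6: 20 of 100 starters and 28 of 108 randomised without the primary endpoint. Gamma is taken as gel minus tamoxifen, so that a positive value is worse for gel, consistent with the null of gamma at or above M.

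**Step 1: the plan's own figure.** The plan states "sample size of $n=40$ evaluable patients per arm will provide 80.5% power with one-sided $\alpha = 0.10$ significance level". SE = 5.4 × √(2/40) = 1.2075. With a true difference of 0 (not stated, but implied by the result), the noncentral t with 78 df gives 80.52%. The figure reproduces.

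**Step 2: what the limits would allow if applied to gamma.** Assume that standardized bias means bias divided by the SE of gamma; the documents do not define it. For a bias of b standard errors toward non-inferiority, at the margin:

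- one-sided error = 1 − Φ(1.2816 − b)
- coverage of a 95% interval = Φ(1.96 − b) − Φ(−1.96 − b)

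| b | Bias (points) | One-sided error | Coverage |
|---|---|---|---|
| 0.10 | 0.12 | 0.119 | 94.9% |
| 0.25 | 0.30 | 0.151 | 94.3% |
| 0.40 | 0.48 | 0.189 | 93.2% |
| 0.44 | 0.53 | 0.200 | 92.8% |
| 0.50 | 0.60 | 0.217 | 92.1% |

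At b = 0.50, 1 − Φ(0.7816) = 0.217; a simulation of 400,000 runs also gave 0.217. Coverage of 92.1% clears the 90% limit, so the second check does not catch the bias. With the same bias against non-inferiority, the error is 1 − Φ(1.7816) = 0.037 and power falls to 64.5%.

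If the denominator were instead the SD of change, the limit would be 0.5 × 5.4 = 2.7 points, which is larger than the margin itself.

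**Step 3: leaving arm out of the model.** If 20% of outcomes are imputed with no arm term, those values carry almost no arm difference. A true difference of 2.6 then becomes about 0.8 × 2.6 = 2.08. The bias of 0.52 points is 0.52/1.2075 = 0.43 of the planning SE, so it would pass a 50% limit.

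Two simulation runs support this (50 per arm, 20% missing at random, true difference 2.6, 20 imputations, Rubin's rules). Each cell gives normal, then skewed Ki-67.

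| Run | Arm in model? | Mean estimate | False non-inferiority |
|---|---|---|---|
| A | no | 2.07, 2.06 | 18.0%, 28.2% |
| A | yes | 2.60, 2.58 | 10.3%, 14.0% |
| B | no | 2.09, 2.05 | 16.6%, 19.0% |
| B | yes | 2.60, 2.58 | 9.2%, 10.3% |

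The shrinkage is stable. The error rate depends on the assumed distribution, and part of the 28.2% is due to skewness, since the model with arm still gives 14.0% there.

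**Step 4: how much is missing.** 20/100 = 20% and 28/108 = 25.9%. Both exceed 10%, but the trigger counts entries, a denominator that the plan does not define.

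**The case against.** The best defence is that this paragraph governs little. Imputation is optional, the main analysis is complete-case, and best-worst and covariate-adjusted analyses would stand beside any imputed result. All of that is correct. Three stronger readings are tempting, and the documents support none of them.

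- *Imputations are accepted because they match the design.* The power-analysis sentence is a stated goal. It is not one of the four listed checks, and no text makes agreement with it a condition of acceptance.
- *The type I error of the trial is doubled.* The 0.217 belongs to an optional secondary analysis. It needs bias over SE as the definition, gamma as the target and bias in the favourable direction, and the plan states none of these. Limits that cannot be computed on the trial's data do not decide the result there either.
- *The model excludes arm.* Arm is not named, but it is a binary variable and nothing rules it out.

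A further objection concerns who is missing. Section 2.3.3 expects 10 to 20 percent of women to have no residual DCIS and keeps them out of the main analysis. Section 3.2 attributes half of the 20% loss to insufficient DCIS tissue, and section 13.4.2 attributes all of it to insufficient residual DCIS. Where no lesion remains, DCIS Ki-67 does not exist and should not be imputed. This stands and it shapes the remedy.

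The defence leaves untouched a goal that is wrong under any reading, limits that cannot be evaluated as written, and a model left open.

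**Conclusion.** The point holds as a fault in the rule for a secondary analysis. The goal sentence is wrong in principle, and this needs no numerical assumption. The bias and coverage limits cannot serve as acceptance criteria on the trial's own data and are not tied to gamma.

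The sizes are conditional. A one-sided error of 0.217 against 0.10 is the worst case under the bias-over-SE reading, with 0.037 if the bias runs the other way. If arm were omitted with 20% imputed, an estimate of about 2.1 for a true 2.6 would be expected. False non-inferiority would be about 17% to 19% in one simulation run and 18% to 28% in the other.

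The primary complete-case test keeps its error rate as far as this text is concerned. What is weakened is the robustness evidence, which matters when 20% to 26% of women are expected to lack the primary endpoint. The change should be made, but the design does not depend on it.

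**What to change.** In section 13.8.2:

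1. Delete the goal sentence, and drop the bias and coverage limits as acceptance criteria.
2. Name multiple imputation as a sensitivity analysis to the complete-case analysis. Fix the model in advance: arm, baseline Ki-67, menopausal status and compliance. State the number of imputations, Rubin's rules, and the same ANCOVA and 2.6-point margin as section 13.4.3.
3. Check the imputations by comparing observed and imputed distributions within each arm.
4. Impute only for women whose DCIS Ki-67 exists but was not measured. Report women with no residual DCIS separately by arm, as sections 1.3 and 13.5 already plan.

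Adding site to the model, or imputing whatever the missing rate, is a matter of preference and is not needed to cure the fault.

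The cost is a short SAP edit, slightly more analysis work and less freedom to choose the imputation model later. No visit, sample or sample-size change follows.
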